#### 9.1.2. Secondary Endpoints

The secondary endpoints for this study are as follows:

- 1. Safety defined as the occurrence of all adverse events measured from the Index Procedure through the 2 Week Post Procedure Follow-up Visit.
  - a. The occurrence of > 2 device-related serious adverse events (SAE) is considered a failure 15 subjects and 1 failure in the second 15 subjects (if applicable).
- 2. Procedure time measured in minutes from the point of scope insertion to the point of scope removal (scope-in / scope-out).
- 3. Device deficiencies defined as an inadequacy of a medical device with respect to its identity, quality, durability, reliability, safety or performance including malfunctions, use errors, and inadequate labelling.

#### 9.2. General Statistical Methods

Descriptive statistics will be used to analyze the Primary and Secondary Endpoints. Data will be presented using means and standard deviations, median, quartiles, and minimum and maximum, as applicable.

Distributions of each continuous variable will be assessed prior to analysis and examined for normality. Data with interval or ratio scales to be analyzed that are not normally distributed will be analyzed using non-parametric statistics..

#### 9.2.1. Number of Subjects per Investigative Site

If one clinical site is used for this study, it will enroll up to 30 subjects. If two clinical sites are used for this study an effort to have similar enrollment at each center will be made (i.e. 7 or 8 subjects at each site for each group of 15).

#### 9.3. Sample Size

This study will enroll up to 30 subjects. Sample size determination is based on WAE Design Control and Validation Procedures.

#### 9.4. Data Analyses

To assess whether the Primary Endpoint is met in each group of 15 subjects (as applicable), Criteria A-E must all pass receive a passing score. The questionnaire attached in Appendix A will be answer during each case to document performance of the Poseidon System relative to Criteria A-E

As defined above, criterion A will be assessed on a pass/fail basis. Only 1 failure in each group of 15 will be allowed; >1 failure will result in failure of criterion A.

Criteria B – E will be assessed using a Likert-scale. After 15 each criterion has been assessed in all subjects, scores will be compiled by calculating a mean Likert-score. To pass, each criterion must have a mean Likert score of >3. A score  $\leq$  3 is considered a failure. The rating of the Likert scale will be as follows:

- A value of 1 = Strongly Disagree
- A value of 2 = Disagree
- A value of 3 = Neutral
- A value of 4 =Agree
- A value of 5 = Strongly Agree

Secondary Endpoints will be analyzed as follows:

- 1. Safety: All adverse events will be collected and assessed for relationship to the study device and/or study procedure, seriousness, and severity. Adverse events will be grouped by type and presented in frequencies. If >2 device related SAEs occur, the endpoint will fail.
- 2. Overall Procedure Time: The mean of all procedure times will be taken. There are no pass/fail criteria for this endpoint.
- 3. Device Deficiencies: All device deficiencies will be collected, grouped by type, relationship to adverse events, and presented in frequencies. There are no pass/fail criteria for this endpoint.

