# 4. Study Endpoints

#### 4.1. Primary Endpoint

The primary endpoint for this study is the assessment that the Poseidon device meets all acceptance criteria for design validation.

- 1. The design of the Poseidon System meets all acceptance criteria for design validation.
  - a. User is able to operate device per the instructions for use. This criterion will be assessed in a pass/fail manner with an allowance of only 1 failure in the first 15 subjects and 1 failure in the second 15 subjects (if applicable).
  - b. User shall not adversely influence typical actuation of a scope during colonoscopy procedure as assessed using a 5-point Likert scale.
  - c. User assessment of functional acceptability of Poseidon device ratchet location as assessed using a 5-point Likert scale.
  - d. User assessment of functional acceptability of Poseidon device intergluteal cleft fit as assessed using a 5-point Likert scale
  - e. The Poseidon System shall minimize passage of fluids through and around the scope lumen when a scope is in the device, as assessed using a 5-point Likert scale.

**NOTE:** Criteria B – E must have a mean Likert score of >3 to pass. The rating of the Likert scale will be as follows:

- A value of 1 = Strongly Disagree
- A value of 2 = Disagree
- A value of 3 = Neutral
- A value of 4 = Agree
- A value of 5 = Strongly Agree

The questionnaire that will be used to assess the Primary Endpoint is attached in Appendix A.

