#### 5.1. Scale and Duration

Up to 30 subjects will be enrolled in this study.

Initially 15 subjects will be enrolled in this study and undergo water-aided colonoscopy with the Poseidon™ System. If the Primary Endpoint and Secondary Endpoint 1 are achieved in the first 15 subjects, the study will be complete.

If the Primary Endpoint or Secondary Endpoint 1 are not achieved, changes to the device design will be made and this protocol will be conducted again in a second group of 15 subjects with updated device. All studies sites and associated IRBs will be notified if the second group of 15 subjects will need to be enrolled.

It is anticipated that enrollment of the first 15 subject will take a period of 2 month. If enrollment of the second 15 subjects is required, it is estimated that device design changes will take 1-2 months, and enrollment of the second group of 15 subjects will take a period of 2 months.

Each subject will be followed for approximately 2 weeks following the procedure. Overall the study take 3-7 months to complete.

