#### 8.4. Index Procedure

#### 8.4.1. *Poseidon Procedure*

All enrolled subjects will undergo water-aided colonoscopy using the Poseidon System for fluid management. The operator of the Poseidon device must be a physician and must have received sufficient training in clinical endoscopic technique.

Investigators will assemble and place the Poseidon System prior to initiating colonoscopy according to the investigational instructions for use .

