#### 9.5. Passing Overall Validation

To pass overall validation in the first 15 subjects, the Primary Endpoint and Secondary Endpoint 1 must receive passing scores. If this is achieved in the first 15 subjects the Poseidon System has passed validation and the study is considered complete. If this is not achieved, design changes to the device are warranted.

Once the design changes are made, the new device will be tested in an additional 15 subjects. The Primary Endpoint and Secondary Endpoint 1 must receive passing scores. If this is achieved in the second 15 subjects, the Poseidon System has passed the validation. If this is not achieved in the second group of 15 subjects the Poseidon System has failed validation.

•

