## 10. Data Management

#### 10.1. Data Collection, Processing, and Review

Subject data will be recorded using electronic CRFs (eCRFs) in a web-based, limited access, electronic data capture (EDC) system.

The clinical database will reside on a production server hosted by the EDC System. All changes made to the clinical data will be captured in an electronic audit trail and available for review by the Sponsor or its representative. The associated software and database have been designed to meet regulatory compliance for deployment as part of a validated system compliant with laws and regulations applicable to the conduct of clinical studies pertaining to the use of electronic records and signatures. Database backups are performed regularly.

The Investigator provides his/her electronic signature on the appropriate electronic case report forms (eCRFs) in compliance with local regulations. Changes to data previously submitted to the Sponsor require a new electronic signature by the Investigator acknowledging and approving the changes.

The Sponsor will perform visual and/or electronic data review to identify possible data discrepancies. Manual and/or automatic queries will be created in the EDC system and will be issued to the site for appropriate response. Site staff will be responsible for resolving all queries in the database.

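### Does leaving the number of device operators open, within each group of 15 and across the two groups, call for a change to the plan?

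*Combined protocol and SAP*

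**What the plan says.** Section 4.1 defines five acceptance criteria. Criterion A is a pass/fail judgement on whether the "User is able to operate device per the instructions for use". Criteria C and D are the user's own assessments. B and E are also Likert items, though no rater is named and E is worded as a property of the device. Under section 9.4 one questionnaire is answered per case. Criterion A tolerates one failure in 15. For B to E, "scores will be compiled by calculating a mean Likert-score", and each mean must exceed 3. All five must pass.

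On operators, section 8.4.1 gives a qualification only: "The operator of the Poseidon device must be a physician and must have received sufficient training in clinical endoscopic technique". Section 9.2.1 spreads subjects over sites, aiming for "7 or 8 subjects at each site for each group of 15" if two sites are used. Section 9.3 gives no calculation: "Sample size determination is based on WAE Design Control and Validation Procedures".

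If the first group fails, section 5.1 says that "this protocol will be conducted again in a second group of 15 subjects with updated device", and section 9.5 adds: "If this is achieved in the second 15 subjects, the Poseidon System has passed the validation". A second failure is final. Sections 5.1 and 7.5 have the sponsor notify the study sites when the second group is needed and when it opens, which points to the same sites but does not settle which physicians take part.

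The supplied text contains neither Appendix A (the questionnaire) nor the sponsor's validation procedures. Either might name the rater or set a number of users.

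**The concern.** The unit that is counted is the subject, but much of what is measured comes from the physician. Fifteen scores from one physician carry that person's habit of scoring high or low, and further cases by the same physician do not average it out. Fifteen scores from several physicians partly do. The planned summaries in sections 9.2 and 9.4 would look the same either way.

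The study is described as not powered, but the result binds: a pass completes validation, a first failure triggers a redesign, and a second failure ends it. Two risks follow. A poor device could pass, or a sound one fail, because of who scored it. And after a first failure, a change of physician could produce a pass without any real improvement. It is natural to ask for the number of operators, a cap on cases each, and the same operators in both groups.

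**Working it through.** **Figures in the plan.** Section 9.3 states no error rate, SD or target, so there is no figure to reproduce. The check is how the stated rules behave.

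**Inputs.** From sections 9.4 and 9.5: 15 cases per group, pass if the mean exceeds 3, at most one failure on criterion A, a second group only after a failed first. Assumed, because the documents give nothing: SD 0.9 between cases of one operator; between-operator SD t = 0.25 / 0.5 / 0.75; true mean 2.5 for a device that should fail and 3.5 for one that should pass.

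**One Likert criterion, one group.** P(pass) = Φ((μ − 3) / √(t²h + 0.9²/15)), where 0.9²/15 = 0.054 and h is the sum of squared case shares: 1 for one operator, (64 + 49)/225 = 0.502 for an 8/7 split, 1/3 for three with five cases each, 1/5 for five with three each. For one operator, μ = 2.5 and t = 0.5: Φ(−0.5/√(0.25 + 0.054)) = Φ(−0.907) = 18%.

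| True mean | Operators | t = 0.25 | t = 0.5 | t = 0.75 |
|---|---|---|---|---|
| 2.5 (wrong pass) | 1 | 7% | 18% | 26% |
| 2.5 | 2 (8/7) | 4% | 12% | 19% |
| 2.5 | 3 | 3% | 9% | 15% |
| 2.5 | 5 | 3% | 6% | 11% |
| 3.5 (right pass) | 1 | 93% | 82% | 74% |
| 3.5 | 3 | 97% | 91% | 85% |

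With t = 0 and μ = 2.5 the result is Φ(−0.5/√0.054) = 1.6% for any number of operators. A simulation with scores rounded to 1–5 agrees within 2.3 percentage points. A second set of assumptions (total SD 1, intra-operator correlation 0.3, true mean 2.7) shows the same pattern: wrong pass 31% with one operator, 22% with three, 18% with five.

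**Criterion A.** Suppose first use of the device is harder. Let k operators each have one first use with failure probability q, and let the other 15 − k uses fail with probability 0.02 (all assumed). The chance of at most one failure in 15 is:

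| q | k = 1 | k = 3 | k = 5 |
|---|---|---|---|
| 10% | 95% | 90% | 85% |
| 20% | 93% | 80% | 66% |
| 30% | 90% | 68% | 46% |

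For a sound device, going from one operator to three therefore gains about 4 / 9 / 11 points on each Likert criterion (across the three values of t) and loses about 4 / 12 / 22 points on criterion A (across the three values of q). The two scales rest on separate assumptions and do not pair up, and all of A to E must pass, so the sign of the net effect is not known.

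**Same or new operator in the second group.** Take one operator per group and a device whose true mean does not change. With the same operator the two group means have correlation t²/(t² + 0.054) = 0.54 / 0.82 / 0.91; with a new operator it is 0. The bivariate normal gives:

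| Per criterion, t = 0.25 / 0.5 / 0.75 | New operator | Same operator |
|---|---|---|
| μ = 2.5: passes group 2 after failing group 1 | 7 / 18 / 26% | 5 / 8 / 7% |
| μ = 3.5: passes group 2 after failing group 1 | 93 / 82 / 74% | 69 / 35 / 21% |
| μ = 3.5: fails both groups | 0.5 / 3.3 / 6.9% | 2.2 / 11.9 / 20.8% |

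For t = 0.5 and a new operator, the last row is (1 − 0.8178)² = 3.3%. Keeping the operator protects against a lucky second rater and equally locks in a harsh one.

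**The site split.** Three operators with five cases each give 5 and 10 cases at two sites unless one physician works at both. That conflicts with the 7 or 8 per site in section 9.2.1.

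**The case for a change.** The strongest case for acting is that a binding decision should not rest on a number nobody has set, and that a few sentences would cost no extra subjects. The data list in section 8.4.2 and the device log in section 13 have no item for the operator, so a listing by operator is not assured. Spreading the ratings lowers both kinds of error on criteria B to E, and the trade-off on criterion A could be read as a reason to choose the number deliberately beforehand.

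Much of that stands: the omission is real, and the direction of the effect on B to E is not in dispute. What does not follow is a particular amendment. A clause that fills in a number but accepts one operator leaves the largest error in the table in place. A clause that demands three needs more trained physicians at one or two sites and may lose on criterion A what it gains elsewhere. A same-operator clause exchanges one error for the other. A listing by operator is useful description but moves no pass/fail result, and section 8.2 already counts procedure notes among source documents, from which the operator should normally be traceable.

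Section 10.1 gives no support for fixing the number early. Its sentence, "The Sponsor will perform visual and/or electronic data review to identify possible data discrepancies", is about data cleaning and has no bearing on who operates.

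**Conclusion.** The supplied text leaves open how many physicians operate and score the device, how many cases each performs, and who does the second group. The dependence on the user is explicit for criteria A, C and D and inferred for B and E. Under the assumed SDs, one operator rather than three raises the chance of a wrong pass on one Likert criterion from 3 / 9 / 15% to 7 / 18 / 26%; if operators do not differ, the number is irrelevant. These figures are per criterion and approximate the primary endpoint only when one criterion is deficient and the others pass. The second-group figures also assume an unchanged device, whereas the plan tests a redesigned one.

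No change to the plan follows. Each remedy that would alter the error rates raises another error or strains the site split, and the remedies without that cost alter no decision. In a small, descriptive design validation this is a detail that those running and reporting the study can supply: say who completed the questionnaire, how many operators there were with how many cases each, and whether they changed between groups.

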#### 9.5. Passing Overall Validation

To pass overall validation in the first 15 subjects, the Primary Endpoint and Secondary Endpoint 1 must receive passing scores. If this is achieved in the first 15 subjects the Poseidon System has passed validation and the study is considered complete. If this is not achieved, design changes to the device are warranted.

Once the design changes are made, the new device will be tested in an additional 15 subjects. The Primary Endpoint and Secondary Endpoint 1 must receive passing scores. If this is achieved in the second 15 subjects, the Poseidon System has passed the validation. If this is not achieved in the second group of 15 subjects the Poseidon System has failed validation.

•

## 9.5.1. Interim Analyses

No interim analyses are planned for this study.

#### 9.5.2. Changes to Planned Analyses

Any changes to the planned statistical analyses made prior to performing the analysis will be documented and approved in this protocol. Changes from the planned statistical methods after performing the final analysis will be documented in the clinical study report along with a reason for the deviation.

## 10. Data Management

#### 10.1. Data Collection, Processing, and Review

Subject data will be recorded using electronic CRFs (eCRFs) in a web-based, limited access, electronic data capture (EDC) system.

The clinical database will reside on a production server hosted by the EDC System. All changes made to the clinical data will be captured in an electronic audit trail and available for review by the Sponsor or its representative. The associated software and database have been designed to meet regulatory compliance for deployment as part of a validated system compliant with laws and regulations applicable to the conduct of clinical studies pertaining to the use of electronic records and signatures. Database backups are performed regularly.

The Investigator provides his/her electronic signature on the appropriate electronic case report forms (eCRFs) in compliance with local regulations. Changes to data previously submitted to the Sponsor require a new electronic signature by the Investigator acknowledging and approving the changes.

The Sponsor will perform visual and/or electronic data review to identify possible data discrepancies. Manual and/or automatic queries will be created in the EDC system and will be issued to the site for appropriate response. Site staff will be responsible for resolving all queries in the database.

#### 10.2. Data Retention

The Principal Investigator or his/her designee or Investigational site will maintain, at the clinical site, all essential study documents and source documentation that support the data collected on the study subjects in compliance with ICH/GCP guidelines. Documents must be retained for at least 2 years after the last approval of a marketing application or until at least 2 years have elapsed since the formal discontinuation of the clinical investigation of the

product. These documents will be retained for a longer period of time by agreement with WAE Medical or in compliance with other country/regional/local regulations.

The Principal Investigator or his/her designee will take measures to ensure that these essential documents are not accidentally damaged or destroyed. If for any reason the Principal Investigator or his/her designee withdraws responsibility for maintaining these essential documents, custody must be transferred to an individual who will assume responsibility and WAE Medical must receive written notification of this custodial change. Sites are required to inform WAE Medical in writing where paper or electronic files are maintained in case files are stored off site and are not readily available.

## 11. Amendments

If a protocol revision is necessary which affects the rights, safety or welfare of the subject or scientific integrity of the data, an amendment is required. Appropriate approvals of the revised protocol must be obtained prior to implementation.

# **12. Protocol Deviations**

An Investigator must not make any changes or deviate from this protocol, except to protect the life and physical well-being of a subject in an emergency. An Investigator shall notify the Sponsor and the reviewing IRB/EC of any deviation from the investigational plan to protect the life or physical well-being of a subject in an emergency, and those deviations which affect the scientific integrity of the clinical investigation. Such notice shall be given as soon as possible, but no later than 5 working days after the emergency occurred, or per prevailing local requirements, if sooner than 5 working days.

All deviations from the investigational plan, with the reason for the deviation and the date of occurrence, must be documented and reported to the Sponsor. Sites may also be required to report deviations to the IRB/EC, per local guidelines and regulations.

Deviations will be reviewed and evaluated on an ongoing basis and, as necessary, appropriate corrective and preventive actions such as site re-training, site enrollment hold or site discontinuation will be put into place by the Sponsor.

# **13. Device Accountability**

Investigational devices from the Sponsor, the devices will only be used for the purpose of this clinical study and they will be maintained in a secure, limited-access area. All investigational devices provided to a clinical site will be labeled with the wording "CAUTION -- Investigational device. Limited by Federal (or United States) law to investigational use." As required by 21 CFR 812.5. Receipt and disposition of these devices shall be kept in the device accountability log for this study.

The Sponsor shall keep records to document the physical location of all study devices from the point of shipment until use, return, or disposal.

Clinical sites that use their own commercial equipment must still track the devices used for the purpose of the study on the device accountability log.

The Principal Investigator or an authorized designee will maintain the device accountability log for this study. The following information will be required for every device:

- Date of receipt (if provided by Sponsor for purpose of clinical study)
- Product ID number
- Serial number of capital equipment
- Lot number of disposable devices
- Expiration date (as applicable)
- Date of device use
- Subject ID number in which the device was used
- Date device was returned to Sponsor (as applicable)
- Reason device was returned to Sponsor (as applicable)

# 14. Compliance

#### 14.1. Statement of Compliance

This post market study will be conducted in accordance with this protocol, ISO 14155, The Declaration of Helsinki, ICH Guidelines for Good Clinical Practices, applicable parts of the US Code of Federal Regulations, and pertinent individual country laws and regulations. The study shall not begin until the required approval/favorable opinion from the IRB/EC is obtained. Any additional requirements imposed by the IRB/EC shall be followed, if appropriate.

